3.6 Risks and benefits

AMG 334 is being developed as for migraine prophylaxis in a large clinical development program including more than 4800 patients. Key risks and benefits are briefly summarized below. For further information, please refer to the most recent Investigator Brochure.

There were no significant findings in the toxicology studies with AMG 334 that would predict a risk to human patients. There were no significant effects on electrocardiogram (ECG) parameters, blood pressure (BP) or respiration rate in the single dose cardiovascular study in cynomolgus monkeys.

As of May 2019, approximately 4817 patients have received at least 1 dose of AMG 334, accounting for approximately 4418 patient-years. To date, no important risk has been identified for AMG 334.

A theoretical cardiovascular safety risk with CGRP pathway blockade is lack of compensatory vasodilation, particularly in the context of the coronary circulation during ischemic-related conditions although there has been no clinical evidence suggesting that selective blockade of the CGRP pathway during ischemia worsens myocardial ischemia to date. Patients in clinical trials will continue to be monitored for cardiovascular effects, and patients with pre-existing cardiovascular disease will be excluded from participation.

All biologicals, including fully human proteins, have the potential to induce immunogenicity leading to the development of specific anti-drug antibodies. So far, the development of anti-AMG 334 antibodies was not associated with specific adverse events or a clinically relevant reduction in AMG 334 plasma levels. Patients in clinical studies will continue to be monitored for the development of anti-AMG 334 antibodies and associated clinical sequelae.

Plasma levels of CGRP increase with advancement of pregnancy up to the time of delivery, followed by a sharp decline at term and postpartum in rats and humans. Endogenous CGRP may play an important role in maintaining normal fetoplacental development, fetal survival, and vascular adaptation during pregnancy. Women who are breastfeeding, pregnant, or planning to become pregnant are excluded from study participation, as well as patients who are unwilling to comply with the protocol-specified contraception requirements. All women of child bearing potential will be screened for pregnancy at each study visit.

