5.5.4 Instructions for prescribing and taking study treatment

Subcutaneous (s.c.) injections are to be given for each investigational product administration. For purposes of study treatment dosing, “q.m.” refers to an every 4 weeks injection regimen. The study drug administration date should be in 4 week increments (+/- 5 days) from the first dose of study drug. Any dose administrations that may occur greater than +/- 5 days from the 4 week time point (e.g., patient unavailability) should be discussed with the Sponsor prior to dosing. The anatomical sites for administration of investigational product are the upper arm, upper thigh, or abdomen; the location of the injection sites should be documented in the source document.

Double-Blind Treatment Epoch:

Two injections of AMG 334 70 mg (equaling 140 mg total dose) or placebo will be administered by qualified study staff at each dosing visit during the 12-week double-blind treatment epoch (i.e., at Day 1 and Weeks 4 and 8).

Open-label Treatment Epoch and PTA-Open-Label Treatment Epoch:

Two injections of open-label AMG 334 70 mg (equaling 140 mg total dose) will be administered by qualified study staff at each dosing visit during the 156-week open-label treatment epoch (ie, at Weeks 12, 16, 20, 24, etc.) and during the PTA-Open-Label Treatment Epoch (ie, at Weeks 168, 172, 176, 180 etc.). If and when 140 mg/mL pre-filled syringes become available during the Open-Label Treatment Epoch, the 140 mg dose may be administered by a single 140 mg/mL s.c. injection.

The investigational product dose is fixed and will not be adjusted for individual patients during the study. There are no temporal restrictions for study drug administration (e.g., proximity to meals, sleep or activity).

All kits of study treatment assigned will be recorded in the IRT. Novartis monitors will reconcile treatment assigned vs treatment administered and ensure that the information is congruent during their monitoring visits.

During the **COVID-19 pandemic** that limits or prevents on-site study visits, delivery of study drug directly to a patient’s home is generally permitted in the event the Investigator has decided that an on-site visit by the patient is no longer appropriate or possible, and that it is in the interest of the patient’s health to administer (e.g., self-injection or study staff administration at patients’

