5.6.2 Discontinuation of study treatment

Discontinuation of study treatment for a patient occurs when study drug is stopped earlier than the protocol planned duration, and can be initiated by either the patient or the investigator.

The investigator must discontinue study treatment for a given patient if, on balance, he/she believes that continuation would negatively impact the risk/benefit of trial participation.

Study treatment must be discontinued under the following circumstances:

- Patient wish
- Pregnancy (see [Section 6.5.6](#) and [Section 7.5](#))
- Use of prohibited treatment as per recommendations in [Table 5-1](#)
- Any situation in which study treatment might result in a safety risk to the patient
- Unsatisfactory therapeutic effect
- Patient's condition no longer requires study treatment
- Any laboratory abnormalities that in the judgment of the investigator, taking into consideration the patient's overall status, prevents the patient from continuing participation in the study

In addition, study treatment should be discontinued under the following circumstances during the PTA- Open-Label Treatment Epoch:

- Upon country-level launch (as specified in [Section 3.1](#))

- Patient is no longer clinically benefitting from treatment in the opinion of the investigator

If discontinuation of study treatment occurs in the Double-Blind Treatment Epoch, the patient should NOT be considered withdrawn from the study, and should continue recording in the eDiary as per protocol. If permanent discontinuation of study treatment occurs during the Open-Label Treatment Epoch or during the PTA-Open-Label Treatment Epoch, the patient should be discontinued from the study.

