5.6.5 Early study termination by the sponsor

The study can be terminated by Novartis at any time for any reason. This may include reasons related to the benefit-risk assessment of participating in the study, practical reasons, or for regulatory or medical reasons (including for example slow enrollment or an unreasonably low number of patients continuing). In the event that the study is terminated early, the IRBs/IECs will be informed. Should this be necessary, the patient must be seen as soon as possible and treated as a prematurely withdrawn patient. The investigator may be informed of additional procedures to be followed in order to ensure that adequate consideration is given to the protection of the patient's interests.

6 Visit schedule and assessments

Table 6-1, Table 6-2, Table 6-3 Table 6-4 and Table 6-5 list all of the assessments and indicate with an "X" when the visits are performed.

Patients must be seen for all visits on the designated day, or as close to it as possible. Missed or rescheduled visits should not lead to automatic discontinuation.

If the **COVID-19 pandemic** limits or prevents on-site study visits, alternative methods of providing continuing care may be implemented. Phone calls, virtual contacts (e.g. teleconsult) or visits by site staff to the patient's home depending on local regulations and capabilities, can replace on-site study visits, for the duration of the pandemic until it is safe for the patient to visit the site again (see Section 6.4 efficacy, Section 6.5.4 Laboratory evaluations, Section 6.5.6 Pregnancy and assessments of fertility, Section 6.6.6 AMG 334 Antibody testing, [REDACTED] Section 7 Safety monitoring and Section 7.6 Prospective suicidality assessment for further COVID-19 guidance related to sample collection).

Table 6-1 Assessment Schedule: Double-Blind Treatment

Epoch	Screen	Baseline ³	Double-Blind Treatment ^{1,4}				Follow-Up ²	Notes	
Visit	1	2	101	102	103	199	301	Follow up visit is 16 weeks after last dose of IMP (V103 / Wk 8), which is 12 weeks after last DBT visit (V199 / Wk 12).	
Week	-6	-4	Day 1	4	8	12/PSD/TD	24/FU		
Obtain Informed Consent	X								
Randomization			X						
Demography	X								
Medical & Medication History	X							Including prior prophylactic migraine medication	
Treatment Failure Confirmation	X								
Complete Physical Exam	S					S	S		
Brief Physical Exam		S	S	S	S				
Height	X								
Weight	X		X			X	X		
Vital Signs ⁵	X	X	X	X	X	X	X		
Chemistry/Hematology	X		X			X	X		

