Clinical Global Impression - Improvement		X	X	X	X	X	X	X
Clinical Global Impression – Efficacy Index		X	X	X	X	X	X	X
Pregnancy test (urine) ¹				X			X	X
PTA-Open-Label Treatment Epoch Completion								X

X Assessment to be recorded in the clinical database or received electronically from a vendor

¹ Results of pregnancy tests will be documented in source documents.

² Once PTA ends in a country the patient should come to the clinic for a final End of Treatment visit (occurs 4 weeks after previous dose)

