6.5 Safety

Safety assessments will include:

- Adverse events ([Section 7.1](#))
- Physical examination
- Vital signs
- Height/Weight

- Laboratory evaluations
- Pregnancy testing (females of childbearing potential)
- ECG
- Columbia Suicide Severity Rating Scale (C-SSRS) ([Section 7.6](#))

The timing and frequency of these assessments are outlined in [Table 6-1](#) , [Table 6-2](#), [Table 6-3](#) [Table 6-4](#) and [Table 6-5](#).

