6.5.6 Pregnancy and assessments of fertility

All pre-menopausal women who are not surgically sterile will have pregnancy testing. Serum pregnancy tests will be performed at the beginning and end of the study, with urine pregnancy tests performed at the remaining visits. The specific schedule is outlined in [Table 6-1](#) , [Table 6-2](#), [Table 6-3](#) , [Table 6-4](#) and [Table 6-5](#).

During COVID-19 pandemic, if a patient cannot visit the site to have pregnancy tests conducted the patient may complete a urine pregnancy test at home and report the result to the site. It is important that patients are instructed to perform the urine pregnancy test first and only if the test result is negative proceed with the administration of the study treatment. A communication process should be established with the patient so that the Site is informed of the pregnancy test results.

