7.6 Prospective suicidality assessment

The Columbia-Suicide Severity Rating Scale (C-SSRS) is a questionnaire that prospectively assesses Suicidal Ideation and Suicidal Behavior. The C-SSRS must be administered at each visit, including unscheduled visits.

A validated version of the C-SSRS will be used to capture self-reported C-SSRS data in a web-based interactive response system (eC-SSRS) via the patient’s eDiary or via the web link. The eC-SSRS uses a detailed branched logic algorithm to perform the C-SSRS patient interview, evaluating each patient’s suicidality ideation and behavior in a consistent manner. At the conclusion of each assessment, the investigator will receive a detailed eC-SSRS Findings Report via e-mail or fax. If the system assesses the patient as having positive suicidal signs, the investigator will be immediately notified by either fax, e-mail and/or via telephone.

If, at any time after screening and/or baseline, the score is “yes” on item 4 or item 5 of the Suicidal Ideation section of the C-SSRS or “yes” on any item of the Suicidal Behavior section, the patient must be referred to a mental health care professional for further assessment and/or treatment. The decision on whether the study treatment should be discontinued is to be taken

by the investigator in consultation with the mental health professional to whom the patient is referred.

In addition, all life-threatening events must be reported as SAEs. For example, if a patient answers “yes” to one of the questions in the Suicidal Behavior section, an SAE must be reported if the event was life-threatening. All events of “Non-Suicidal Self-Injurious Behavior” (question also included in the Suicidal Behavior section) should be reported as AEs and assigned the appropriate severity grade.

All SAEs relating to suicidal behavior must be reviewed by the Safety Management Team or early project teams.

During the **COVID-19 pandemic** that limits or prevents on-site study visits, the eC-SSRS may still be collected via the patient’s eDiary or via the web link.

8 Data review and database management

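### Table 6-5 schedules a urine pregnancy test at only one of every three post-trial access doses, while Protocol 3.6 promises screening at every visit

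*Protocol*

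**What the plan says.** **Pregnancy testing.** Protocol 3.6 sets the rule without exception: "All women of child bearing potential will be screened for pregnancy at each study visit". Section 6.5.6 gives the general pattern, "Serum pregnancy tests will be performed at the beginning and end of the study, with urine pregnancy tests performed at the remaining visits", and then sends the reader to Tables 6-1 to 6-5 for the specific schedule. Its COVID-19 paragraph tells patients who test at home to test first and to take the dose only after a negative result. Table 6-5 marks drug at Visit 299 and Visits 401 to 406, and a urine test at 403, 406 and 499 only. A footnote keeps the results in source documents.

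**Consequence of a pregnancy.** Section 5.6.2 lists pregnancy under "Study treatment must be discontinued under the following circumstances".

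**Entry to PTA.** Section 3.1 allows a treatment gap between the two open-label periods, during which the patient stays in the study.

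**Suicidality.** Section 7.6 says: "The C-SSRS must be administered at each visit, including unscheduled visits". Section 6.5 includes the C-SSRS in its list of safety assessments and says of that list: "The timing and frequency of these assessments are outlined in" Tables 6-1 to 6-5. Table 6-5 as available to this review has no C-SSRS row.

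**Follow-up.** Section 5.6.2 names Tables 6-1, 6-4 and 6-5 for the visit about 16 weeks after the last dose. Section 5.6.1 names only Tables 6-1 and 6-4 for the same visit (Visit 301).

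**The concern.** The protocol makes a safety commitment in its risk-benefit section that its own PTA schedule does not deliver. Section 3.6 explains why the commitment is there: CGRP, whose receptor the drug blocks, may matter for fetal survival and development. A site that works from Table 6-5, as sites usually do, gives most PTA doses without a scheduled test. A pregnancy could then go undetected for longer than 3.6 implies, while dosing continues that 5.6.2 would require to stop.

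The treatment gap adds to this. A patient may return to drug after an interval off study treatment, and Table 6-5 marks no test before Visit 403. Any test done at Visit 299 under Table 6-4 could by then be out of date.

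The C-SSRS raises the same kind of question: the text requires it at every visit, and the PTA table does not show it.

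**Working it through.** The plan states no figure for this point, so the check is a count of marks in Table 6-5 against the text, followed by a calendar check on how many doses a patient can receive.

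**1. Marks in Table 6-5**

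| Visit | Week | Drug | Urine test |
|---|---|---|---|
| 401 | 172 | X | none |
| 402 | 176 | X | none |
| 403 | 180 | X | X |
| 404 | 184 | X | none |
| 405 | 188 | X | none |
| 406 | 192 | X | X |
| 499 | 4 weeks after previous dose | none | X |

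Dosing visits 401 to 406: 6. With a test: 2. Without: 6 − 2 = 4, at Visits 401, 402, 404 and 405. Share without a test = 4/6, or two in each three-dose cycle. Visit 299 (week 168) is left out because it is also the closing visit of open-label year 3, and Table 6-4 is not in the text available here.

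**2. Longest run between scheduled tests**

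192 − 180 = 12 weeks, with doses at weeks 184 and 188 in between. A pregnancy that begins just after the week-180 test could be exposed to 2 further doses before the next scheduled test.

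**3. How many of these doses the calendar allows**

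Inputs: first patient screened 20 March 2017 and enrollment complete 6 July 2017 (Amendment 3 rationale); Baseline Epoch of 4 weeks and PTA ending by December 2020 (3.1). Assumptions: the last patient's Day 1 is 6 July 2017, there is no treatment gap, and the limit falls between 1 and 31 December 2020.

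- Last patient: 6 July 2017 + 168 weeks = 24 September 2020. To 31 December is 98 days = 14 weeks, so doses at weeks 172, 176 and 180 fit and week 184 (16 weeks on) does not. Doses without a scheduled test: 2. To 1 December is 68 days = 9.7 weeks, so only weeks 172 and 176 fit, again 2 without a test.
- Four untested doses require reaching week 188 (1,316 days). That needs Day 1 by 25 May 2017 for a 31 December limit, or by 25 April 2017 for a 1 December limit.
- Earliest possible Day 1: 20 March 2017 + 4 weeks = 17 April 2017. From then to 6 July is 81 days inclusive, of which 81 − 39 = 42 fall after 25 May. So even on the generous limit, just over half of the window leads to fewer than four.
- Week 192 needs Day 1 by 27 April 2017 for a 31 December limit, so only the earliest patients could get there. For a 1 December limit the date is 28 March 2017, before anyone could have been randomised.

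A treatment gap or a country launch shortens all of this further.

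**4. C-SSRS**

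Visits 401 to 406 and 499 make 7 visits, and the C-SSRS is marked at 0 of 7. Table 6-5 carries no visible redaction mark, and the C-SSRS row is present in Tables 6-1 and 6-2.

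**5. Follow-up pointer**

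Table 6-5 ends at Visit 499, 4 weeks after the previous dose. The follow-up is due at 16 weeks, that is 16 − 4 = 12 weeks later, and has no column there. Table 6-1 does have a Visit 301 column.

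**The case against.** The best defence is that the tables govern. Section 6 says that the tables "list all of the assessments and indicate with an" X, 6.5 sends timing to them, and 6.5.6 names Table 6-5 among the specific schedules directly after its general sentence. One test per three-month cycle also looks intended. This stands for 6.5.6, and it makes a deliberate lighter schedule plausible. It does not answer 3.6, which defers to no table and has no PTA exception, and nothing in the protocol says which prevails.

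A reader might infer that sites cannot comply with both text and table. That goes too far: testing at every visit would satisfy both.

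A reader might also infer that the scheduled test is the only route to stopping treatment. It is not. Under 5.6.2 pregnancy itself is the reason, however it is detected. The contraception requirement, 24-hour pregnancy reporting (7.5) and adverse event collection at every PTA visit all remain. These reduce the risk but do not replace the test that 3.6 promises.

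Comparison with the early epochs carries little weight. Every visit in Tables 6-1 and 6-2 has a pregnancy test, but the Amendment 3 rationale describes a reduced schedule after open-label year 1, and Tables 6-3 and 6-4 are not available here.

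On the C-SSRS, a row can be lost in extraction without a trace. Table 6-1 shows no BDI-II row although exclusion criterion 12 needs a screening score. Loss is not the likeliest explanation, but it cannot be excluded.

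**Conclusion.** The inconsistency between 3.6 and Table 6-5 is real and should be corrected. Two of every three doses in a complete PTA cycle have no scheduled pregnancy test, with a ceiling of four over Visits 401 to 406 and about two for the last patients randomised. The per-patient counts rest on the calendar assumptions above; the count of marks in the table does not. The number of women of child-bearing potential in PTA is not given, so the total number of doses concerned cannot be stated.

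The point is more than clerical for three reasons: pregnancy is a mandatory stop, the home-testing guidance in 6.5.6 treats the test as a gate to the dose, and 3.1 allows a gap before PTA dosing resumes.

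The C-SSRS discrepancy is secondary and held with medium confidence. The follow-up reference in 5.6.2 is editorial. A reader might infer from it that PTA patients have no safety follow-up, but 5.6.1 requires Visit 301 for those who do not continue on drug, and Table 6-1 gives its content. The absence of an exam row in Table 6-5, against the brief exam at all visits in 6.5.1, is also editorial.

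None of this bears on the double-blind comparison, the efficacy analyses or the safety variables in 9.5.2.

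**What to change.** 1. **Pregnancy test.** Add a pre-dose urine test at Visits 401, 402, 404 and 405 in Table 6-5, and repeat the pattern in later cycles. Cost: up to four kits per woman over Visits 401 to 406. Results stay in source documents, so no database change or extra visit is needed.
2. **If quarterly testing is intended**, write an explicit PTA exception with its rationale into 3.6 and 6.5.6, and still require a test before the first PTA dose after any treatment gap. Cost: two sentences and at most one kit per woman returning from a gap.
3. **C-SSRS.** Add the electronic form at Visits 401 to 406 and 499, or state a PTA exception in 7.6. Cost: seven questionnaires per patient who attends all of these visits, or one sentence. Section 7.6 already provides for completion by web link.
4. **Editorial.** In 5.6.2, point PTA patients to the Visit 301 column of Table 6-1 or 6-4, and note a PTA exception for the brief exam in 6.5.1. One sentence each.

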4.1 Inclusion criteria

Patients eligible for inclusion in this study must fulfill all of the following criteria. For inclusion purposes, one month equals one calendar month.

During the Screening Epoch:

1. Written informed consent must be obtained before any assessment is performed
2. Adults ≥ 18 to ≤ 65 years of age upon entry into screening
3. Documented history of migraine (with or without aura) for ≥ 12 months prior to screening according to the [International Classification of Headache Disorders-12rd Edition \(ICHD-3\)](#)
4. 4 to 14 days per month (in at least two separate attacks) of migraine symptoms (based on [ICHD-3](#) criteria) on average across the 3 months prior to screening based on retrospective reporting
5. < 15 days per month of headache symptoms (ie migraine and non-migraine)

Patients must have*:

6. Failed 2 to 4 prior migraine prophylaxis treatments out of the following:
 - Propranolol/metoprolol, topiramate, flunarizine, valproate/divalproex, amitriptyline, venlafaxine, lisinopril, candesartan, locally approved products (e.g. oxeterone or pizotifen)
7. Failed one AND failed *or* not be suitable for a second of the following:
 - Propranolol OR metoprolol
 - Topiramate
 - Flunarizine
8. Failed *or* not be suitable for valproate or divalproex

* The following definitions are applicable for inclusion criteria 6-8:

- Efficacy failure is defined as “no meaningful reduction in headache frequency after administration of the respective medication for an adequate period of time (at least 2-3 months are recommended by the European Headache Federation treatment guidelines) at generally accepted therapeutic dose(s) based on the investigator’s assessment within the last 5 years prior to screening.”
- Tolerability failure is defined as “documented discontinuation due to adverse events of the respective medication at any previous time.”
- “Not suitable” for the purpose of this study is defined as “patient is not considered to be suitable for the treatment for medical reasons such as contraindications or precautions included in local labels, national guidelines or other locally binding

documents, or other medically relevant reasons” as confirmed by the treating physician.

During the Baseline Epoch:

9. Migraine frequency of 4 to 14 migraine days during the Baseline Epoch, confirmed by the eDiary
10. $\geq 80\%$ eDiary compliance during the Baseline Epoch

